### **7.15 Quantitative Computed Tomography (QCT)**

A subset of the subjects participating in the Imaging and PK/BTM/Biomarker sub-study will undergo QCT scans of the spine at visits specified in [Section 7.3](#) and the Schedule of Assessments ([Appendix A](#)).

The same QCT scanner must be used for all scans for a particular subject. All QCT scans will be collected by a trained technician and submitted to the central imaging vendor for analysis. QCT data are considered potentially unblinding and will not be reported to study-related personnel (including sites) post Day 1/baseline. Detailed instructions for scan acquisition are provided in a separate manual by the central imaging vendor.

### **7.16 Biomarker Development**

#### **7.16.1 Biomarker Development**

Biomarkers are objectively measured and evaluated indicators of normal biologic processes, pathogenic processes, or pharmacologic responses to a therapeutic intervention. Biomarker development may be useful in developing markers to identify disease subtypes, guide therapy, and/or predict disease severity.

Amgen may attempt to develop blood tests designed to identify subjects most likely to respond positively or negatively to romosozumab. Biomarker development may be pursued by use of advanced biochemical analyses, such as proteomic methods or ribonucleic acid transcript profiling.

If informed consent is provided by the subject, blood samples will be collected for biomarker development at the time points specified in the Schedule of Assessments ([Appendix A](#)).

Refer to the laboratory manual for detailed collection and handling procedures for biomarker development samples.

### **7.16.2 Sample Storage and Destruction**

Biomarker development blood samples and any other components from the cells, as well as any other unused samples may be stored for up to 20 years from the end of the study to research scientific questions related to osteoporosis in postmenopausal women and/or romosozumab. The subject retains the right to request that the sample material be destroyed at any time by contacting the principal investigator. The sponsor will be the exclusive owner of any data, discoveries, or derivative materials from the sample materials and is responsible for the destruction of the sample(s) at the request of the subject through the principal investigator or at the end of the storage period or as appropriate (eg, the scientific rationale for experimentation with a certain sample type no longer justifies keeping the sample). Following the request from the subject, the principal investigator will provide the sponsor with the required study and subject numbers so that any remaining blood samples and any other components from the cells can be located and destroyed. If a commercial product is developed from this research project, the sponsor will own the commercial product. The subject will have no commercial rights to such product and will have no commercial rights to the data, information, discoveries, or derivative materials gained or produced from the sample. See [Section 11.3](#) for subject confidentiality.

## **8. REMOVAL AND REPLACEMENT OF SUBJECTS**

### **8.1 Removal of Subjects**

Subjects have the right to withdraw fully or partially from the study at any time and for any reason without prejudice to his or her future medical care by the physician or at the institution.

Withdrawal of full consent for a study means that the subject does not wish to receive further investigational treatment and does not wish to or is unable to continue further study participation; subject data and samples obtained up to withdrawal of consent will be included in the analysis of the study. Any subject may withdraw full consent to participate in the study at any time during the study. The investigator will discuss with the subject appropriate procedures for withdrawal from the study.

Withdrawal of partial consent for a study means that the subject does not wish to take investigational product(s) or other protocol-required therapies any longer but is still willing to collaborate in providing further data by continuing on study (eg, participate in all

subsequent study visits or procedures). Subjects may decline to continue receiving investigational product(s) or other protocol-required therapies at any time during the study. If this occurs, the investigator will discuss with the subject appropriate procedures for withdrawal from investigational product(s) or other protocol-required therapies. These subjects, as well as those who have stopped receiving investigational product(s) or other protocol-required therapies for other reasons (eg, investigator or sponsor concern) should continue the schedule of study observations.

Should a subject (or a legally acceptable representative) request or decide to withdraw from the study, all efforts will be made to complete and report the observations as thoroughly as possible up to the date of withdrawal. All information should be reported on the applicable eCRFs.

Reasons for removal from protocol required products or observation might include:

- partial withdrawal of consent
- withdrawal of full consent
- administrative decision by the investigator or Amgen
- pregnancy in a female subject (report on Pregnancy Notification Worksheet; see [Appendix C](#)).
- ineligibility
- significant protocol deviation
- subject noncompliance
- adverse event
- disease progression
- other safety concern by the investigator or Amgen
- death
- lost to follow-up

If a subject experiences BMD reduction of  $\geq 7\%$  from baseline at the total hip and/or lumbar spine at any time during the primary analysis period, the investigator is required to discuss implications for individual fracture risk, alternative treatment options and options for continuing in the study with the subject, and to document that discussion. If a decision is made to begin alternative treatment, IP must be discontinued and every effort should be made to complete all remaining study visits, regardless of any alternative treatment chosen by the subject.

## **8.2 Replacement of Subjects**

Subjects will not be replaced on this study.

---

## **9. SAFETY DATA COLLECTION, RECORDING, AND REPORTING**

### **9.1 Adverse Events**

#### **9.1.1 Definition of Adverse Events**

An adverse event is defined as any untoward medical occurrence in a clinical trial subject. The event does not necessarily have a causal relationship with study treatment. The investigator is responsible for ensuring that any adverse events observed by the investigator or reported by the subject are recorded in the subject's medical record.

The definition of adverse events includes worsening of a pre-existing medical condition. Worsening indicates the pre-existing medical condition (eg, diabetes, migraine headaches, gout) has increased in severity, frequency, and/or duration, and/or has an association with a significantly worse outcome. A pre-existing condition that has not worsened during the study, and involves an intervention such as elective cosmetic surgery or a medical procedure while on study is not considered an adverse event.

#### **9.1.2 Reporting Procedures for Adverse Events**

The investigator is responsible for ensuring that all adverse events observed by the investigator or reported by the subject that occur after the first dose of IP through the end of study are reported using the applicable eCRF (eg, Adverse Event Summary eCRF). For subjects who discontinue the study early, adverse events will be reported through 30 days after the last dose of IP.

The investigator must assign the following adverse event attributes:

- Adverse event diagnosis or syndrome(s), if known (if not known, signs or symptoms),
- Dates of onset and resolution,
- Severity (and/or toxicity per protocol),
- Assessment of relatedness to IP, and
- Action taken.

The adverse event toxicity grading scale used will be the Common Terminology Criteria for Adverse Events (CTCAE) version 3.0. The toxicity grading scale used in this study is described in [Appendix B](#).

The investigator must assess whether the adverse event is possibly related to the IP and/or other study drugs. This relationship is indicated by a "yes" or "no" response to the question: Is there a reasonable possibility that the event may have been caused by the IP and/or other study drugs?

The investigator must assess whether the serious adverse event is possibly related to any study-mandated screening procedure. This relationship is indicated by a “yes” or “no” response to the question: “Is there a reasonable possibility that the event may be related to screening procedures?”

The investigator must assess whether the adverse event is possibly related to any study-mandated activity or procedure. This relationship is indicated by a “yes” or “no” response to the question: “Is there a reasonable possibility that the event may have been caused by a study activity/procedure”?

The investigator is responsible for reviewing laboratory test results and determining whether an abnormal value in an individual study subject represents a clinically significant change from the subject’s baseline values. In general, abnormal laboratory findings without clinical significance (based on the investigator’s judgment) should not be recorded as adverse events. However, laboratory value changes that require treatment or adjustment in current therapy are considered adverse events. Where applicable, clinical sequelae (not the laboratory abnormality) should be recorded as the adverse event.

The investigator is expected to follow reported adverse events until stabilization or reversibility.

The investigator’s clinical judgment will be used to determine whether a subject should be removed from treatment or from the study due to an adverse event. A subject, or subject’s parent/legal guardian, may also voluntarily withdraw from treatment due to an adverse event. If the subject withdraws full consent, the subject should be encouraged to undergo, at a minimum, an end-of-study assessment.

## **9.2 Serious Adverse Events**

### **9.2.1 Definition of Serious Adverse Events**

A serious adverse event is defined as an adverse event that meets at least 1 of the following serious criteria:

- fatal
- life threatening (places the subject at immediate risk of death)
- requires in-patient hospitalization or prolongation of existing hospitalization
- results in persistent or significant disability/incapacity
- congenital anomaly/birth defect
- other medically important serious event

An adverse event would meet the criterion of “requires hospitalization”, if the event necessitated an admission to a health care facility (eg, overnight stay).

If an investigator considers an event to be clinically important, but it does not meet any of the serious criteria, the event could be classified as a serious adverse event under the criterion of “other medically important serious event”. Examples of such events could include allergic bronchospasm, convulsions, blood dyscrasias, DILI (see [Appendix B](#) for drug-induced liver injury reporting criteria), or events that necessitate an emergency room visit, outpatient surgery, or urgent intervention.

### **9.2.2 Reporting Procedures for Serious Adverse Events**

The investigator is responsible for ensuring that all serious adverse events observed by the investigator or reported by the subject that occur after signing of the informed consent through 30 days after the last dose of IP are recorded in the subject’s medical record and are submitted to Amgen. For subjects who discontinue the study early, serious adverse events will be reported through 30 days after the last dose of IP. The serious adverse event must be submitted to Amgen within 24 hours following the investigator’s knowledge of the event. If the electronic data capture (EDC) system is unavailable to the site staff to report the Serious Adverse Event, the information is to be reported to Amgen via an electronic Serious Adverse Event (eSAE) Contingency Report Form within 24 hours of the investigator’s knowledge of the event. See [Appendix D](#) for a sample of the Serious Adverse Event Worksheet/eSAE Contingency Report Form. Where the first notification of a Serious Adverse Event is reported to Amgen via the eSAE Contingency Report Form, the data must be entered into the EDC system when the system is again available.

The investigator is expected to follow reported serious adverse events until stabilization or reversibility.

In addition to the attributes listed in [Section 9.1.2](#), the investigator must also complete the SAE section of the Adverse Event Summary CRF.

After the protocol-required reporting period defined above, the investigator does not need to actively monitor subjects for serious adverse events. However, if the investigator becomes aware of a serious adverse event after this protocol-required reporting period, the investigator will report the event to Amgen within 24 hours following the investigator’s knowledge of the event. SAEs reported outside of the

protocol-required reporting period will be captured within the safety database as clinical trial cases for the purposes of expedited reporting.

New information relating to a previously reported serious adverse event must be submitted to Amgen. All new information for serious adverse events must be sent to Amgen within 24 hours following the investigator's knowledge of the new information. The investigator may be asked to provide additional follow-up information, which may include a discharge summary or extracts from the medical record. Information provided about the serious adverse event must be consistent with that recorded on the applicable eCRF (eg, Adverse Event Summary eCRF).

If a subject is permanently withdrawn from protocol-required therapies because of a serious adverse event, this information must be submitted to Amgen.

To comply with worldwide reporting regulations for serious adverse events, the treatment assignment of subjects who develop serious, unexpected, and related adverse events may be unblinded by Amgen before submission to regulatory authorities. Investigators will receive notification of related serious adverse events reports sent to regulatory authorities in accordance with local requirements.

Amgen will report serious adverse events and/or suspected unexpected serious adverse reactions as required to regulatory authorities, investigators/institutions, and IRBs/ECs in compliance with all reporting requirements according to local regulations and good clinical practice (GCP).

The investigator is to notify the appropriate IRB/EC of serious adverse events occurring at the site and other adverse event reports received from Amgen, in accordance with local procedures and statutes.

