#### Potential Cardiovascular Events

In order to carefully evaluate cardiovascular events during the trials, all deaths, and serious adverse events that are deemed by the investigator to be of potential cardiovascular origin or etiology, will be submitted to an independent committee for adjudication. Serious adverse events with terms mapping to a pre-defined preferred term list potentially indicative of cardiovascular etiology will also be adjudicated.

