 11. Blood draws for BTMs must be obtained from subjects in fasting stage and before noon. Fasting stage is defined as overnight fasting. If overnight fasting is not feasible, at a minimum 8 hours is required.

12. SAE reporting to continue through 30 days after the last dose of IP.
13. Monthly contacts begin at M13. Contact will be initiated by a phone call. During the primary analysis period, if back pain is reported during the phone call, it will be recorded as an adverse event and the subject will be asked to complete an unscheduled follow-up clinic visit as soon as possible but no later than 21 days after reporting of the back pain for evaluation of a suspected clinical vertebral fracture.
14. Lateral spine x-ray will only be taken at the unscheduled follow-up clinic visit if the investigator considers the back pain previously reported during the monthly phone contact to be possibly due to a new or worsening vertebral fracture.
15. To facilitate subject scheduling, the Day 1/baseline lumbar spine DXA scan may be taken with the proximal femur DXA scan performed during screening. For Screening and Day 1 purposes, lateral spine x-rays and DXA scans of the lumbar spine and proximal femur taken up to 35 days prior to the beginning of the screening period may be used if all of the criteria outlined in [Section 7.2.1](#) are met.
16. In a subset of subjects.
17. To be processed and sent to the central laboratory during the primary analysis period; to be analyzed at local laboratories following the primary analysis period.
18. To be performed in the primary analysis period only.
19. To be performed at month 36 and then every 12 months thereafter during the primary analysis period only.
20. For subjects in the sub-study only.

Notes:

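### Protocol 9.1.2 and 9.2.2 give conflicting end dates for serious adverse events in women who stop all investigational product but remain on study, and the route of later events to the clinical database and adjudication is not stated

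*Protocol*

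**What the plan says.** - **Adverse events (Protocol 9.1.2).** The investigator must ensure that all adverse events that "occur after the first dose of IP through the end of study are reported using the applicable eCRF". There is one exception: "For subjects who discontinue the study early, adverse events will be reported through 30 days after the last dose of IP".
- **Serious adverse events (Protocol 9.2.2).** The investigator records and submits SAEs "that occur after signing of the informed consent through 30 days after the last dose of IP". After that there is no duty to look for SAEs, but any that come to the investigator's knowledge must be reported within 24 hours. These late reports are held in the safety database to serve expedited reporting.
- **Schedule (Protocol Appendix A).** Footnote 12 is attached to the adverse event row and reads "SAE reporting to continue through 30 days after the last dose of IP".
- **Definition (Protocol 9.2.1).** "A serious adverse event is defined as an adverse event that meets at least 1 of the following serious criteria".
- **Subjects off IP (Protocol 8.1).** Women who have stopped IP "should continue the schedule of study observations". Section 6.5 and the BMD-loss rule in 8.1 also ask for continued follow-up of women who come off IP.
- **Cardiovascular adjudication (Protocol 7.9).** The committee receives "all deaths, and serious adverse events that are deemed by the investigator to be of potential cardiovascular origin", and also SAEs that match a predefined term list. SAP 10.6.3 has the same scope. Neither states a window tied to the last dose.
- **Analysis (SAP 7.5 and 10.6).** Events are counted by study period. After the double-blind period, women with at least one open-label alendronate dose contribute their events up to the end of the period. Women who stay on study without open-label alendronate have their later events listed.

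**The concern.** For a woman off IP but on study, the SAE rule closes earlier than the rule for adverse events in general, so the more serious class of event has the shorter required window. A site that follows the more specific SAE rule can say that it complies with the protocol while not actively looking for, say, a non-fatal stroke three months after the last dose.

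This matters because non-fatal cardiovascular adjudication is fed by SAEs. An event that is not sought, is not flagged as serious, or sits only in the safety database may not reach the committee. It would then be absent from the incidence rates and odds ratios planned in SAP 10.6.3. If stopping IP differs between arms, the shortfall could differ too. The documents give no figure for stopping by arm, so this is a possibility and not a finding.

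**Working it through.** No power, event count or alpha level bears on this point, and the plan states no figure to reproduce. The check is a comparison of texts.

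**1. Do the two windows conflict?** By group of subject:

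| Subject | 9.1.2: all adverse events | 9.2.2 and footnote 12: SAEs | Conflict |
|---|---|---|---|
| On IP to end of study | End of study | Last dose + 30 days | No practical gap |
| Leaves the study early | Last dose + 30 days | Last dose + 30 days | No |
| Stops all IP, stays on study | End of study | Last dose + 30 days | **Yes** |

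The definition in 9.2.1 places SAEs inside the set of adverse events. In the third row the same event therefore has two end dates. Section 9.2.2 goes on to give early leavers a 30-day limit. In 9.1.2 that sentence is a real exception to the general rule; in 9.2.2 it only repeats it. This suggests a drafting slip.

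**2. Who is in the third row?** Protocol Section 6 counts alendronate as IP, so stopping the injections alone does not close the window. The group is women off both injection and tablets who remain under observation, which the protocol asks of them in 6.5 and 8.1.

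**3. Does the analysis use the time after the window?** Yes, in two ways.
- A woman who stops everything before Month 12 still contributes to the 12-month safety comparison up to the end of the double-blind period.
- A woman who takes at least one open-label dose and later stops contributes up to the end of the primary analysis or overall study period.

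A woman who never takes open-label alendronate adds nothing to incidence rates after the double-blind period. Her later events are only listed (SAP 10.6).

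**4. Where do late SAEs go?** Section 9.2.2 names the safety database. SAP 9.1 takes the study data from the EDC database. No passage says that late SAEs are entered there or forwarded under 7.9.

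**5. How long can the gap be for one woman?** The last-dose month *m* is an assumption. The SAE window closes at about *m* + 1 months. Follow-up comes from the 25 to 59 months in Protocol 3.4.1, less about 1 month of screening, giving 24 to 58 months. Time on study outside the window is follow-up − (*m* + 1):

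| Assumed *m* | 24 months' follow-up | 58 months' follow-up |
|---|---|---|
| 6 | 24 − 7 = 17 months | 58 − 7 = 51 months |
| 12 | 24 − 13 = 11 months | 58 − 13 = 45 months |

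Within the 12-month comparison, *m* = 6 leaves about 12 − 7 = 5 months outside. These figures are time per woman outside the SAE window. They do not count missed events.

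**The case against.** The strongest reply is that nothing is lost in practice.

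- Section 9.1.2 covers all adverse events, and SAEs are adverse events, so serious events are still required on the eCRF to end of study.
- Any later SAE the investigator learns of must be reported within 24 hours.
- Learning of it is likely. Adverse events are collected from all subjects, with no on-IP condition, at clinic visits and at monthly telephone contacts to end of study (Protocol 7.3.20).
- All deaths go to adjudication, and no adjudication trigger carries a last-dose window.

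Most of this stands, and it limits the point. A reader might infer that women off IP drop out of SAE capture and cardiovascular adjudication altogether, or that deaths will be missed. The documents do not support that: 9.1.2 still applies to these women, 9.2.2 keeps a duty to report, and Protocol 7.9 and SAP 10.6.3 send every death to the committee.

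A reader might also attach a size by assuming that 10–20% of 4,000 women spend 1–2 years off IP. That gives 400 to 1,600 subject-years, or about 3–13% of roughly 12,000 (4,000 × 3 years). None of the percentages or durations is in the documents, and the result is time off drug, not missed events.

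The reply does not remove the conflict. Footnote 12 sits on the adverse event row itself, so the schedule carries the shorter limit at the place where sites look. The duty to report late SAEs depends on the investigator learning of them, and it leads to a database that the SAP does not name as a source.

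**Conclusion.** The point holds as a conflict between sections with a limited consequence. Sections 9.1.2 and 9.2.2, the latter with footnote 12, cannot both be the rule for serious events in women who stop all IP and stay on study. The safety analysis counts by study period and so relies on the longer rule, while the SAE procedure asks for the shorter one. Late non-fatal serious events, cardiovascular ones included, may be captured and adjudicated less completely than the analysis assumes.

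The size cannot be given. It depends on how many women are off IP but on study, for how long, and whether this differs by arm, and the documents state none of these. A bias between arms is possible but not shown. The change should still be made: this is a stated rule that permits less complete capture of serious events, which is more than a missing detail.

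**What to change.** Reconcile Protocol 9.2.2 and Appendix A footnote 12 with 9.1.2:

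- For every subject remaining on study, SAE reporting runs through end of study, or through 30 days after the last dose if that is later.
- The 30-day limit for subjects who leave the study early stays as the exception, as in 9.1.2.
- One added sentence states that these SAEs are entered on the eCRF and, where they meet the triggers in 7.9, sent for adjudication.

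The cost is amendment wording and some extra SAE reporting and adjudication work. The burden is small, because sites already contact these women and collect their adverse events to end of study. The SAP counting rules need no change.
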